## The timetable of study activities

**Table 1. Timing of activities in Cohort 1 (2-dose scheme)**

No. of visit	1	2	3	4		
Objective of visit	Screening Dose 1, Blood sampling §	Blood sampling from a subset of subjects§	Blood sampling from a subset of subjects §	Blood sampling §	End of monitoring efficacy	End of monitoring adverse events
Month	Month 1			Month 2	Month 4	Month 6
Day	0	5	28	56		
Acceptable interval (open window period) 		+ 2	+ 7	+ 7		
Informed consent Complete eCRF (demographic info, concurrent treatments, history of underlying conditions, etc.)	•					
Blood sampling to assess the previous infection of COVID-19 (antibody assay)	•					
Physical examination 	•		•			
Randomization	•					
Intervention						
Vaccine injection and active monitoring for 0.5 hours after the shot	•		•			
Evaluation of vaccine efficacy						
Monitoring of symptomatic COVID-19 cases (ex-program visit) 	•					
Blood sampling	•			•		
Safety evaluation						
Handover of diary form to volunteers 	•		•			

Returning and reviewing of Diary form			•	•		
Recording adverse event	•					
Recording AEs which need medical intervention and those end up with study stop Recording those interventions (treatments) for AEs	•					
Recording SAEs and their related treatments	•					
Recording other treatments and vaccines during the study period 	•					

§ Among cities under the two-dose scheme (Cohort), just Sari and Babol will do serologic assays for all volunteers on days 0 and 56 and 30% of subjects on day 5 and another 30% on day 28.

1) Window period means an acceptable interval that a volunteer can come for a visit or to receive the intervention

2) A comprehensive physical examination encompasses measuring vital signs, height and weight on day 0. Before every vaccine shot, the volunteer's arm is inspected for regional lymph nodes. Every significant physical finding must be reported as a side event that needs medical intervention. Vital signs will be assessed before vaccination on days 0 and 28. Febrile subjects on day 0 (the 1st dose of vaccine) will be excluded (a temperature beyond 38°C is defined as fever). Those volunteers having fever on day 28 (the 2nd dose of vaccine) will be rescheduled for an alternative date (within the window period) to get their 2nd shot.

All volunteers will be instructed to coordinate with the call center and go to designated laboratories for a PCR test quickly within 48 hours in case of presenting with two or more of the following symptoms lasting for over 24 hours confirmed in positive PCR testing: Fever (temperature  $\geq 38^{\circ}\text{C}$ ), chills, new cough, sore throat, nasal congestion, fatigue, muscle or body pain, headache, nausea or vomiting, diarrhea, loss of smell or taste, or at least one respiratory sign or symptom (i.e., cough, O2 saturation  $< 91$ , shortness of breath, or clinical or radiographic evidence of pneumonia).

3) Nasopharyngeal and pharyngeal swabs will be taken from the symptomatic volunteer. If the volunteer cannot be present in the lab, the operator arranges a home visit/s for him/her to take samples and clinical assessment/s. If the home visit is impossible, the symptomatic volunteer is asked to make a pharyngeal gargle with a standard method and then bring it to the lab. If PCR turns to be negative yet the symptoms last for more than 2 days, the test will be repeated after 7 days. The volunteers with positive tests who do not need hospitalization will be visited by Phone daily until full recovery of symptoms. It is important

to take note that some manifestations of COVID-19 have overlapped with systemic AEs following immunization (e.g., myalgia, headache, fever and chills). Regarding that such AEs are more common within 3 days following vaccination in case of having other symptoms of COVID-19, an infectious disease specialist judges clinically and decides whether a sample for PCR is needed. All PCR-positive cases after the 2nd shot will be counted and included to estimate vaccine efficacy (primary outcome).

4) The volunteer must record all solicited local and systemic AEs within the first 72 hours post-vaccination in their online profiles. If any volunteer did not complete the diary, an active follow-up will be done on day four. Moreover, unsolicited adverse events will be followed up 28 days after each dose, and medically attended adverse events and serious adverse events will be monitored six months after the first dose.

5) All medical treatments and other vaccines received within the 28 days after each vaccine dose as well as AEs and SAEs will be recorded. All SAEs which need medical intervention will be recorded from screening day (Day 0) till the end of follow-up (6 months after the first dose).

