### **3.1 Patient Recruitment**

**3.1.1 First stage:** We will invite the public via social networks, text messages, and media. Our trained staff will define the objectives of the study and inclusion criteria for participants and make sure that everyone understands them. Further information will be available on the recruiting website. Participants can register on the website after assessing the eligibility criteria. The required registration items will be the city name, national ID number, phone number, and history of underlying disease(s). Healthy people with chronic conditions that are under control (diabetes, liver or renal disease, and hypertension) can participate in the study after a complete examination by the study physician and laboratory results in the following range:

- Chronic renal disease (GFR > 30 CC/min calculated based on the blood creatinine level)
- Chronic liver disease (AST < 100 U/L, ALT < 150 U/L)
- Type 2 diabetes mellitus (HbA1C < 7.5%)
- Hypertension (Systolic blood pressure < 140 mmHg and diastolic blood pressure < 90 mmHg on medication based on self-declaration and on-site vital sign assessment)

**3.1.2 Second stage:** The eligible volunteers will receive preliminary approval by a text message containing the appointment date, time, and address of the vaccination

**3.1.3 Third stage (visit 1):** In case of any ambiguity about the situation, volunteers can ask further questions from research physicians.

After taking the informed consent in two copies, the physician will examine the volunteers and order further screening or laboratory analyses. All consenting participants will be screened for underlying chronic conditions and COVID-19-related clinical symptoms. Then volunteers will receive a unique randomization ID that helps them to check their vaccination status until the end of the study.

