#### **4.3 Safety Assessment**

Whether solicited or unsolicited, the local and systemic adverse events (AEs) will be recorded in diary forms by the volunteers. The AEs will be recorded from the first dose (Day 0) until five months after the last dose in both cohorts.

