#### **4.3.1 Adverse Events (AEs)**

The AE is defined as any untoward medical events in participants that are temporally associated with the use of study interventions, whether or not considered related to vaccine/placebo. An AE can vary from clinical manifestations to abnormal test results.

After each injection, systemic and local pre-defined AEs will be registered using an online platform within three days. Solicited local AEs occur in the injection site and include pain, redness, swelling, induration, and warmth. Solicited systemic AEs are fever, chills, nausea, vomiting, malaise, fatigue, headache, diarrhea, pain in extremities, and rashes. Participants will record all these events using an online platform within three days after receiving each dose of vaccine or placebo. If any volunteer will not complete the diary, an active follow-up will be done on day four. Moreover, other unspecified symptoms (unsolicited AEs) will be followed up 28 days after each injection.

Serious Adverse Events (SAEs) are defined as any event which leads to a dangerous situation, hospitalization, longer duration of hospital stays, serious/permanent disability, congenital anomalies, requires a medical or surgical intervention to prevent permanent injury, or culminates in death. These events will be monitored up to five months after the last dosage of vaccine/placebo.

Medically Attended AEs (MAAEs) are adverse events after taking intervention that requires presentation to a health care provider, such as a general practitioner or emergency room visit for physical examinations. These events will be monitored up to five months after the last dosage of vaccine/placebo.

For monitoring and managing of AEs, the following measures will be performed:

- Active monitoring of participants for adverse events for half an hour after receiving each dose at vaccination sites.
- An Emergency medical services (EMS) ambulance will stand with three paramedics. There is an attending emergency medicine specialist with all first-aid and resuscitation equipment in place

All arrangements and coordination have been made with a supporting hospital in each city to transfer and visit participants who might suffer SAEs. In case of any SAE, the emergency specialists of the study will coordinate with the hospital an appointment for participants. We will provide 24-hour free-of-charge medical services in these hospitals for participants during the study.

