- The solicited AEs (local and systemic) are recorded in online diary forms up to 72 hours after receiving each dose by volunteers. If any volunteer does not complete the diary, an active follow-up will be done on day fourth. During this period, medical services and consultations, and hospitalization are provided to volunteers who are affected by AEs.
- Passive monitoring of unsolicited AEs from the first day until day 28th is done through spontaneous reporting by participants to call centers or go to specified hospitals.
- SAEs and MAAEs are detected passively whenever a volunteer report to the call center or consults with the hospital. These participants will be followed actively until fully recovered.
- All SAEs and MAAEs should be reported at the earliest time possible (a few days) to the sponsor and PI, who will inform DSMB to decide about unmasking and withdrawing the participants from the study.
- In case of any SAE or fatal event that needs hospitalization, the CoPIs will report the case to the Pasteur Institute of Iran via an urgent phone call, which in turn reports to FDA, and the National Ethics Committee (NEC).

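### Note 2 of Tables 1 and 2 makes every significant physical finding a reportable event needing intervention, even before the first dose, which conflicts with sections 4.3 and 4.3.1

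*Protocol*

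**What the plan says.** Note 2 of Table 1 (Cohort 1) begins with the examination itself: "A comprehensive physical examination encompasses measuring vital signs, height and weight on day 0". It continues: "Before every vaccine shot, the volunteer's arm is inspected for regional lymph nodes". It then gives the reporting rule: "Every significant physical finding must be reported as a side event that needs medical intervention". Note 2 of Table 2 (Cohort 2) carries the same rule. Both tables mark a physical examination at every dosing visit, including Day 0.

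The safety sections set different limits:

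- Section 4.3 on the recording window: "The AEs will be recorded from the first dose (Day 0) until five months after the last dose in both cohorts".
- Section 4.3.1 on what an adverse event is: "any untoward medical events in participants that are temporally associated with the use of study interventions".
- Section 4.3.1 on the medically attended class: "Medically Attended AEs (MAAEs) are adverse events after taking intervention that requires presentation to a health care provider".

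Section 3.1 (third stage) places consent, examination and screening first, and only after them: "Then volunteers will receive a unique randomization ID that helps them to check their vaccination status until the end of the study". The Day 0 examination therefore comes before allocation and before any dose.

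**The concern.** Read as written, note 2 tells site staff to file a finding from the Day 0 examination as an event, although nothing has yet been injected. Such a finding cannot be an adverse event under 4.3.1, and it falls before the window in 4.3 opens.

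The note has a second fault that applies after dosing as well. It puts every significant finding in the class that needs medical intervention, without asking whether anyone intervened or a provider was needed. Section 4.3.1 reserves the medically attended class for events that do require a provider.

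At stake is the cleanness of the unsolicited and medically attended counts in a trial of 24,000 people. Findings made before randomization say nothing about the vaccine, but they add to the count in each arm.

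**Working it through.** **Step 1. Set the rules side by side.**

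| Question | Note 2, Tables 1 and 2 | Sections 4.3 and 4.3.1 |
|---|---|---|
| When can an event arise? | Any examination, Day 0 pre-dose included | From the first dose |
| Must it relate in time to the intervention? | Not asked | Yes |
| When does it count as needing care? | Always, if significant | When it requires a health care provider |
| Is there an exception for pre-existing findings? | None | Implied by the definition, not spelled out |

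**Step 2. See whether the rest of the protocol settles it.** It does not.

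- The safety row of the secondary outcomes table starts at Day 0.
- Table 1 note 5 and Table 2 note 6 start the recording of serious events needing intervention at the screening day.
- Screening, examination, randomization and dose 1 all belong to the Day 0 visit, so an onset date alone cannot separate a pre-dose finding from a post-dose event.
- The Day 0 eCRF entry takes the history of underlying conditions, but nothing directs examination findings there.
- In both tables, the row for adverse events needing medical intervention is marked from Day 0. Its wording is close to that of note 2.

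**Step 3. Work out what following note 2 would do to the comparison.** The protocol has no safety figure to reproduce. Let b be the share of dosed volunteers with a reported Day 0 finding. It has the same expected value in both arms, because the finding precedes randomization. Let p_v and p_c be the true post-dose rates on vaccine and placebo, count each volunteer once, and take findings and events as independent.

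- Observed rate in an arm = 1 − (1 − p)(1 − b)
- Observed risk difference = (1 − b)(p_v − p_c)
- Observed ratio = [1 − (1 − p_v)(1 − b)] / [1 − (1 − p_c)(1 − b)]
- 95% half-width for the difference = 1.96 × √[v(1 − v)/n_v + c(1 − c)/n_c], where v and c are the observed rates

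The arm sizes are from section 6.1: 14,400 and 3,600 in C1, 4,800 and 1,200 in C2. **The rates are assumptions used only to show direction:** p_v = 2%, p_c = 1%, b from 0 to 10%.

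| b | Vaccine | Placebo | Ratio | Difference (points) | Half-width C1 | Half-width C2 |
|---|---|---|---|---|---|---|
| 0 | 2.00% | 1.00% | 2.00 | 1.00 | 0.40 | 0.69 |
| 1% | 2.98% | 1.99% | 1.50 | 0.99 | 0.53 | 0.93 |
| 5% | 6.90% | 5.95% | 1.16 | 0.95 | 0.88 | 1.52 |
| 10% | 11.80% | 10.90% | 1.08 | 0.90 | 1.15 | 1.99 |

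As a check at b = 5%: vaccine 1 − 0.98 × 0.95 = 0.0690, placebo 1 − 0.99 × 0.95 = 0.0595, ratio 0.0690/0.0595 = 1.16, difference 0.95 × 1.00 = 0.95 points.

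The ratio falls quickly, the interval widens, and the difference shrinks only by the factor 1 − b.

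**Step 4. Bound the exposure.** Solicited events come from post-dose diaries and do not pass through note 2. Only unsolicited or medically attended counts can be affected.

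**The case against.** The strongest reply is that the definitions govern and the note is loosely worded.

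- A pre-dose finding is neither an adverse event nor a medically attended event under 4.3.1, so a careful coder would leave it out.
- The secondary outcomes table lists the sources of safety data as the case investigation form, the diary and telephone follow-up. Section 4.3.1 collects unsolicited and medically attended events passively. The examination is not a listed source.
- Fever on Day 0, or blood pressure above 140/90, keeps a volunteer out before dosing, so those findings never reach a comparison that requires at least one dose (6.2.3).
- Several of the conditions admitted under the note to 2.3, such as COPD, ischaemic heart disease and past malignancy, would usually be known from history rather than from vital signs and an arm inspection.
- A full rule for counting treatment-emergent events is commonly left to the statistical analysis plan.

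Much of this stands. It means the protocol does not establish that baseline disease enters the counts, or that many dosed volunteers would have a reportable Day 0 finding. It does not remove the conflict: the note is an explicit order to sites, it says every, and other entries start at Day 0 or screening. Nor does it touch the second fault, the automatic class of needing intervention at later visits.

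Three stronger readings are tempting and should not be drawn:

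- **That the rule masks a true vaccine excess.** Pre-randomization findings are balanced in expectation and the risk difference is nearly kept.
- **That a loss of power can be quoted.** Section 6.3 plans frequencies with 95% intervals in each arm and states no safety test, margin or power. Any power figure would rest on assumed rates and on the choice of variance formula.
- **That pre-dose findings would go to the DSMB for unmasking decisions.** The reporting route is for serious and medically attended events ("All SAEs and MAAEs should be reported at the earliest time possible (a few days) to the sponsor and PI, who will inform DSMB"), and a pre-dose finding is not medically attended under 4.3.1.

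**Conclusion.** The concern holds as an unreconciled contradiction in a stated reporting rule. Note 2 of both tables, taken literally, requires pre-dose findings to be filed as events and puts every later significant finding in the needing-intervention class without assessment. Sections 4.3 and 4.3.1 say otherwise, and nothing else in the protocol decides between them.

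The consequence is conditional on sites following the note. In that case the vaccine/placebo ratio for unsolicited or medically attended events is diluted and the intervals widen. No size can be given: the protocol states neither a rate of significant Day 0 findings nor an adverse event rate, and the table above only shows direction. It assumes equal baseline shares in the arms, independence, and one count per volunteer. The point is modest, but it is more than missing detail, because the text gives sites an instruction that its own definitions do not allow.

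**What to change.** Reconcile note 2 in both tables with 4.3 and 4.3.1. The replacement sentence should say that:

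1. findings at the Day 0 pre-dose examination are recorded as baseline or medical history;
2. a finding at a later examination is reported as an adverse event only if it is new or worse than at Day 0;
3. the medically attended or needing-intervention class is used only when the 4.3.1 definition is met.

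The cost is a small edit to two table notes and to the eCRF instructions. It needs no new visits, data or participants. The raw event count becomes smaller, which should be explained if counts before and after the change are set side by side. How treatment-emergent events are tabulated can stay with the statistical analysis plan.

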**Table 2. Timing of activities in C2 (3-dose regimen)**

No. of visit	1	2	3	4		
Objective of visit	Screening Dose 1 Blood sampling from 2000 subjects of Zanjan city §	Dose 2	Dose 3	Blood sampling from 2000 subjects of Zanjan city §	End of monitoring efficacy	End of monitoring adverse events
Month	Month 1		Month 2	Month 3	Month 5	Month 7
Day	0	28	56	84		
Acceptable interval (open window period) 	0	+ 7	+ 7	+ 7		
Informed consent Complete eCRF (demographic info, concurrent treatments, history of underlying conditions, etc.)	•					
Blood sampling to assess the previous infection of COVID-19 (Antibody assay)	•					
Physical examination 	•	•	•			
Randomization	•					
Intervention						
Vaccine injection and active monitoring for 0.5 hours after the shot	•	•	•			
Evaluation of vaccine efficacy						
Monitoring of symptomatic COVID-19 (ex-program visit) 	•					
Blood sampling 	•			•		

Safety evaluation						
Handover of diary form to volunteers 	●	●	●			
Returning and review of Diary form 		●	●	●		
Recording adverse event	●					
Recording AEs which need medical intervention and those end up with study stop Recording those interventions (treatments) for AEs 	●					
Recording SAEs and their related treatments 	●					
Recording other treatments and vaccines during the study period 	●					

§ Two cities of Zanjan and Yazd follow the three-dose scheme. Just in Zanjan city, blood samples will be taken for serologic assays from 2000 volunteers on days 0 and 84.

- 1) Window period means an acceptable interval that a volunteer can come for visit or to receive the intervention
- 2) A comprehensive physical examination encompasses the measurement of vital signs, height and weight on day 0. Before every vaccine shot, the volunteer's arm is inspected for regional lymph nodes. Every significant physical finding must be reported as a side event that needs medical intervention. Vital signs will be assessed before vaccination on days 0, 28 and 56. Febrile subjects on day 0 (the 1st dose of vaccine) will be excluded (a temperature beyond 38oC is defined as fever). Those volunteers having fever on days 28 and 56 (the 2nd dose of vaccine) reschedule for an alternative date (within the window period) to get their 2nd and 3rd shots.
- 3) All volunteers will be instructed to coordinate with the call center and go to designated laboratories for PCR tests quickly within 48 h. Nasopharyngeal and pharyngeal swabs will be taken from the symptomatic volunteer. If the volunteer cannot be present in the lab, the operator arranges a home visit/s for him/her to take samples and clinical assessment/s. If a home visit is impossible, the symptomatic volunteer is asked to make a pharyngeal gurgle with a standard method and then bring it to the lab. If PCR turns to be negative yet the symptoms last for more than 2 days, the test will be repeated after 7 days. The volunteers with positive tests who do not need hospitalization will be visited by Phone daily until full

recovery of symptoms. It is important to take note that some manifestations of COVID-19 have overlapped with systemic AEs following immunization (e.g., myalgia, headache, fever and chills). Regarding that such AEs are more common within 3 days following vaccination in case of having other symptoms of COVID-19, an infectious disease specialist judges clinically and decides whether a sample for PCR is needed. All PCR-positive cases after the 2nd shot will be counted and included for the estimation of vaccine efficacy (primary outcome).

4) Blood samples will be taken from 2,000 volunteers in Zanjan city for serologic assay on days 0 and 84.

5) The volunteer must record all solicited local and systemic AEs within the first 72 hours post-vaccination in their online profiles. If any volunteer did not complete the diary, an active follow-up will be done on day four. Moreover, unsolicited adverse events will be followed up 28 days after each dose, and medically attended adverse events and serious adverse events will be monitored for seven months after the first dose.

6) All medical treatments and other vaccines received within the 28 days after each vaccine dose as well as AEs and SAEs will be recorded. All SAEs which need medical intervention will be recorded from screening day (Day 0) till the end of follow-up (7 months after the first dose).

